## **Statement of Compliance**

This study will be conducted in accordance with the Code of Federal Regulations on the Protection of Human Subjects (45 CFR Part 46), 21 CFR Parts 50, 56, 312, and 812 as applicable, any other applicable US government research regulations, and institutional research policies and procedures. The International Conference on Harmonisation (“ICH”) Guideline for Good Clinical Practice (“GCP”) (sometimes referred to as “ICH-GCP” or “E6”) will be applied only to the extent that it is compatible with FDA and DHHS regulations. The Principal Investigator will assure that no deviation from, or changes to the protocol will take place without prior agreement from the sponsor and documented approval from the Institutional Review Board (IRB), except where necessary to eliminate an immediate hazard(s) to the trial participants. All personnel involved in the conduct of this study have completed Human Subjects Protection Training.

## List of Abbreviations

AE	Adverse Event/Adverse Experience
BUP	Buprenorphine
BUP/NX	Buprenorphine/Naloxone
CFR	Code of Federal Regulations
COWS	Clinical Opioid Withdrawal Scale
CRF	Case Report Form
CSOC	Clinical Study Oversight Committee
DCC	Data Coordinating Center
DEA	Drug Enforcement Administration
DHHS	Department of Health and Human Services
DSMB	Data and Safety Monitoring Board
DSM-5	Diagnostic and Statistical Manual
ED	Emergency Department
EQ-5D-3L	EuroQol 5 dimensions, 3 rd level
FFR	Federal Financial Report
FWA	Federalwide Assurance
FDA	Food and Drug Administration
GCP	Good Clinical Practice
HIPAA	Health Insurance Portability and Accountability Act
ICF	Informed Consent Form
ICH	International Conference on Harmonisation
IRB	Institutional Review Board
ISM	Independent Safety Monitor
LFTs	Liver function tests (AST, ALT)
MOP	Manual of Procedures
N	Number (typically refers to participants)
NIH	National Institutes of Health
NYULH	New York University Langone Health
OHRP	Office for Human Research Protections
OHSR	Office of Human Subjects Research
PI	Principal Investigator
QA	Quality Assurance
QC	Quality Control
SAE	Serious Adverse Event/Serious Adverse Experience
SOP	Standard Operating Procedure
US	United States

## Protocol Summary

Title	Buprenorphine Loading in the Emergency Department
Short Title	BUP LOAD-ED
Brief Summary	
Buprenorphine (BUP) is FDA-approved for the treatment of opioid withdrawal and opioid use disorder. Prior studies have demonstrated feasibility, safety, and efficacy of Emergency Department (ED)-initiated BUP, but there are many barriers to widespread implementation of this intervention. Few ED providers have received the necessary DEA registration (aka X-waiver) required to prescribe BUP, and urgent appointments to continue ongoing BUP treatment may not be readily available, thus leading to medication discontinuity. A loading dose induction strategy with 32mg of BUP may help effectively link ED patients to outpatient treatment while minimizing known barriers to ED uptake. Administering a loading dose of BUP to saturate mu-opioid receptors would extend the duration of action, therefore providing additional time to secure ongoing treatment. Further, BUP's ceiling effect on respiratory depression makes it a remarkably safe drug even at high doses. In recent years, ED providers have begun to incorporate this approach into clinical protocols; however, it has not been formally studied in this clinical setting. Our study represents the necessary step of studying this novel approach in the ED setting to define the parameters for clinical protocols and large-scale studies.

Phase	Phase IV
Objectives	

1. To evaluate the feasibility, acceptability, safety and utility of a BUP 32mg sublingual (SL) loading dose induction strategy in the ED.

2. To determine optimal processes for an ED protocol and clinical trial.

Methodology	
This is an open-label, single arm study in which 35 ED patient-participants who have untreated moderate to severe opioid use disorder (OUD) and are experiencing opioid withdrawal will receive treatment with BUP 32mg SL along with referral for ongoing treatment. Assessments will occur in-person on days 0-3 and by phone on day 30, to assess the feasibility, acceptability, safety, and utility of this clinical intervention primarily by assessing its effect and the duration of effect on opioid withdrawal, craving, and sedation as well as evaluating engagement in ongoing treatment.

Endpoint	
For the primary and secondary objectives, standardized and validated instruments will be used to measure the following: opioid and other illicit drug use using the timeline follow back method and urine or saliva drug screen (UDS); opioid withdrawal and craving using objective and subjective opioid withdrawal scales (e.g. COWS and SOWS) and visual analogue scales (VAS); level of awareness/sedation using the Richmond Agitation Sedation Scale (RASS), patient reported outcomes of quality of life and functional status using the PROMIS Global 10 and Treatment Effectiveness Assessment (TEA); healthcare utilization using the non-study treatment service use form, participant satisfaction and perceived utility of ED-initiated intervention. Engagement in treatment will be assessed by self-report and/or confirmed by treatment provider. An adverse event log will be maintained.

Study Duration	Duration: 7-10 months
Participant Duration	1 month

Population	Eligible participants will be recruited from the Bellevue Hospital ED and NYULH EDs, which have a large proportion of patients with opioid use disorder (OUD), among other substance use disorders (SUD). Individuals can be selected to participate if they are 18 years and older, speak English, meet DSM-5 criteria for moderate to severe OUD, have used opioids within 7 days, have not used methadone at a dose greater than 30mg within 72 hours or 10mg within 24hours, have objective signs of opioid withdrawal with a COWS score $\geq 8$ or are expected to have a score of this level during their ED visit, are willing and able to participate, and have adequate locator information including access to a phone. Patients will be excluded if they are currently engaged in medication treatment for OUD (methadone, BUP, or naltrexone), are prescribed opioids for treatment of pain, cognitively impaired, in police custody, have an allergy to BUP, receive a dose of BUP greater than 8mg before study enrollment, or have acute medical or psychiatric conditions or co- occurring substance use disorders that are deemed to preclude safe participation, such as recent methadone use. Subjects will also be excluded if they do not have reliable access to a phone or if a 3-hour observation period in the ED is not feasible (may be limited by provider or patient availability).
Study Sites	The study will take place in the Emergency Departments at Bellevue Hospital and NYU Langone Health sites including NYULH-Tisch, NYULH-Brooklyn, NYULH-Winthrop, and NYULH-Cobble Hill.
Number of participants	35 participants
Description of Study Agent/Procedure	BUP 32 mg SL (in two doses of 8mg and 24mg)
Key Procedures	Urine or saliva test, administration of BUP 32 mg SL.
Statistical Analysis	Statistical analyses will consist of descriptive analyses and will provide summary tabulations and measures of central tendency, variance, and other distributional properties of the obtained results. Where applicable, we will also conduct cross-tabulations and comparative analyses of variance based on selected key characteristics of the study participants (e.g., sex, age categories, withdrawal scores at baseline).

### 1.1.1 Schedule of Research Events

	Research Visits				
	Index	Day 1	Day 2	Day 3	Day 30
Eligibility and Enrollment					
Potential participants identified by staff referral and/or research staff screening	x				
Approval of clinical provider (confirmation that medically and psychiatrically stable and appropriate for study participation)	x				
Written Informed Consent and Medical Release	x				
Eligibility Assessments and Checklist (DSM-5 OUD, Medical exam, COWS)*	x				
Assessments					
Demographics (PhenX)	x				
Drug Use Inventory and other Substance Use Measures (PhenX, TLFB)	x	x	x	x	x
Urine and/or Saliva Toxicology (Standard panel, BUP, FEN)	x				
Withdrawal and Craving Measures (COWS, SOWS, scales)*	x	x	x	x	x
Quality of life and treatment (PROMIS-GLOBAL- 10, TEA)	x	x	x	x	x
Overdose and risk assessments	x	x	x	x	x
Qualitative Assessments/Participant Satisfaction	x	x	x	x	x
Non-Study Medical and Other Services (NMS)	x	x	x	x	x
Adverse Events	x	x	x	x	x
Administrative Actions and Review					
Appointment scheduling for research visits and follow up care	x	x	x	x	
Participant compensation (value)	80	40	40	40	40
Round Trip Metrocard	x	x	x	x	
Healthcare Utilization Review		x	x	x	

\*Multiple assessments conducted before BUP dose 1, after BUP dose 1, and after BUP dose 2

Study Number: s19-01700

Version: 7.0

Version Date: 08/01/2022

## 2 Introduction, Background Information and Scientific Rationale

### ***Background Information and Relevant Literature***

Effective treatments to reduce morbidity and mortality associated with opioid use disorder (OUD) are known, yet few individuals are provided access to these treatments. Narrowing the treatment gap by expanding access to treatment beyond specialized drug treatment settings is a widely accepted public health priority. For many reasons, the Emergency Department (ED) is a logical point of intervention: 1) There is a disproportionately high and growing prevalence of OUD among ED patients; ED visits associated with opioids doubled between 2004 and 2014, and visits for opioid overdose increased by approximately 30% from July 2016 through September 2017; 2) Both multiple ED visits and surviving an overdose are strong predictors for subsequent overdoses and even death; 3) For many individuals, the ED is the primary or only access point in the healthcare system, and, therefore, treatment; 4) The ED visit may represent a critical, time-sensitive moment of motivation for treatment. This context provides a unique opportunity for interventions addressing OUD to gain entry into the ED; however, there is a need to translate treatment approaches to interventions that are feasible and effective in the ED setting.

The landmark trial conducted by D'Onofrio et al. demonstrated the feasibility, safety, and efficacy of ED-initiated buprenorphine (BUP) in the Yale-New Haven Hospital ED. Despite this success, few EDs have adopted this intervention. ED providers often cite time and resource limitations. Widespread implementation is difficult, as few ED providers have received the necessary DEA registration (aka X-waiver) required to prescribe BUP and appointments for linkage to ongoing care within 24 hours may not be readily available. Even in an optimized system, other factors such as problems with medication pre-authorization may delay access. Thus, a critical barrier to ED-initiated BUP is ensuring patients have access to ongoing treatment with BUP without medication discontinuity.

**A novel induction strategy, in which a loading dose of Buprenorphine (BUP) 32mg is administered, has the potential to mitigate this barrier.** ED providers can treat patients with BUP for opioid withdrawal since DEA registration (X-waiver) is not required unless they wish to issue a prescription. Current BUP induction protocols, developed for inpatient and ambulatory care settings as well as for unobserved self-administration via prescription, usually recommend a first day dose of 8mg given in divided doses of 2-4mg. However, patients discharged with  $\leq$  8mg SL total dose may experience return of withdrawal symptoms and/or opioid craving within only 4 hours. Treatment with a loading dose of 32mg in the ED may provide the necessary bridge treatment, relieving symptoms of withdrawal until a patient is able to attend a follow up appointment for further treatment.

Translating existing strategies by taking advantage of the unique and well-established pharmacological properties of BUP has the potential to alleviate the aforementioned barriers to ED-initiated BUP. Demonstrating that this efficacious pharmacotherapy can be initiated practically in the ED as a bridge to ongoing BUP treatment would support efforts to expand the delivery and impact of evidence-based opioid treatment. Further assessment is needed to define the clinical parameters for this induction strategy before incorporating it into clinical protocols and large-scale studies. Our proposal represents the necessary first step in studying this novel approach in the ED setting.

Study Number: s19-01700

Version: 7.0

Version Date: 08/01/2022

### ***Name and Description of the Investigational Agent***

Buprenorphine (BUP) is a lipophilic thebaine derivative with a high binding affinity at the mu-opioid receptor where it has partial agonist effects and at the kappa opioid receptor where it is a competitive antagonist. Like many opioids, BUP was initially commercially developed as an analgesic. In October 2002, the FDA approved BUP for detoxification and maintenance treatment of opioid dependence. For these indications BUP is marketed as Subutex® (Reckitt Benckiser), and in a 4:1 ratio combination with naloxone (BUP-NX), as Suboxone® (Reckitt Benckiser). The BUP-NX combination was developed to limit abuse liability and diversion. Generic formulations of BUP-NX are now available. Recently Reckitt Benckiser began marketing a sublingual BUP-NX film. In this document, we refer to BUP-NX as either BUP-NX or BUP. All study participants will be treated with BUP-NX formulations, though this document may refer to the study drug as simply “BUP”.

BUP was first proposed as an alternative to methadone for treatment of opioid dependence in 1978 and has been studied extensively since. As reported by Jasinski, Mello, and Mendelson, buprenorphine has a low physical abuse potential and a high potential to substitute for heroin and reduce heroin self-administration. These clinical studies suggested that BUP could be used safely and effectively used for pharmacotherapy in clinical settings, but formal approval for clinical use required systematic data on safety and efficacy of BUP when used in larger groups. A set of clinical trials were designed to evaluate the utility from a medication development perspective, and subsequent trials, compared buprenorphine to methadone; evaluated dose comparisons using dose response; and compared buprenorphine to placebo.

Numerous clinical trials involving thousands of participants, have overwhelmingly established both the efficacy and effectiveness of BUP-NX in the community. BUP and BUP-NX are safe and effective alternatives to methadone and enable significant and substantial improvement over time in psychosocial functioning.

Maximal drug effects typically occur at approximately 8 to 16 mg, although sublingual daily doses up to 32 mg have been safely administered for a period of up to a year. Variability in individual dosing addresses the range and severity of opioid dependence across patients. Because of BUP’s lipophilicity and high affinity to the mu-opioid receptor, less-frequent-than-daily dosing is possible for some patients. BUP’s slow dissociation from mu-opioid receptors contributes to its long duration of action and smooth day-to-day course, and minimizes symptoms and signs of withdrawal upon cessation.

**Prescribing and Safety:** Details on BUP-NX (Suboxone®) prescribing, pharmacokinetics and pharmacodynamics, metabolism and elimination, safety and toxicity are described in the Suboxone package insert submitted with this protocol.

#### **2.1.1 Preclinical Data**

See package insert.

#### **2.1.2 Clinical Data to Date**

A small handful of studies to date have demonstrated the safety and effectiveness of high dose BUP induction, ranging from case reports to randomized controlled trials. Ang-Lee et al. observed a significant mean reduction in Clinical Opioid Withdrawal Scale (COWS) score in heroin-dependent patients using 24 mg SL BUP. Furthermore, participants in this small open-label study did not experience any significant adverse events, aside from one participant who had precipitated withdrawal which resolved within 4 hours, and withdrawal suppression lasted >72 hours. A similar study by Kutz et al. treated 10 heroin-users in acute withdrawal with 32 mg BUP (8mg every 5 minutes for 20 minutes), and reported that nine of the participants completed detoxification with negligible withdrawal symptoms, with suppression also lasting > 3- 4 days. Again, no adverse events were reported.

Within the past two years, four randomized controlled trials out of Iran have provided evidence that high dose BUP for opioid withdrawal is both safe and reduces craving/withdrawal over an extended time frame following initial administration. One of these studies randomized 90 opioid-dependent men in withdrawal to three groups to receive single doses of 32 mg, 64 mg, and 96 mg respectively. They observed a significant reduction in craving symptoms using a Visual Analogue Scale (VAS) in all three cohorts that was more pronounced at 64 mg than 32 mg, but no greater effect was observed at 96 mg. The resolution of craving was maintained at 5 days post initial treatment. Only four participants developed side effects, which included hypotension, nausea and vomiting (expected side effects of BUP even at low doses), all of which resolved with hydration and anti-emetics. This research group also published a recent case report of heroin detoxification using 120 mg SL BUP in a single patient experiencing severe withdrawal. Withdrawal suppression persisted for 4 days after initial administration, and the patient was discharged without need for additional buprenorphine. There were no side effects or adverse events reported in this case.

Of note, the other studies out of Iran specifically investigated the effectiveness of single, high dose buprenorphine in mitigating suicidal ideation/depressive symptoms in patient with concurrent opioid use disorder during withdrawal. Nonetheless, they provide support for its safety in single high doses at initiation.

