In ED patients, return of withdrawal symptoms and opioid craving during the high-risk period after discharge but before formal linkage to care likely promotes early return to illicit opioid use and failure to engage in OUD treatment. A SL dose of 4mg achieves a plasma BUP concentration sufficient to suppress craving and withdrawal for  $\leq 2$  hours; a SL dose of 8mg provides  $\leq 4$  hours of therapeutic effect. A 32mg SL dose of BUP may provide effective treatment for over 24 hours or more. The dosage of BUP SL 32mg being used in this study has been approved by the FDA for the treatment of OUD for daily use in the maintenance phase.

ED-initiated BUP induction dosing potentially influences patient satisfaction and retention in opioid use disorder (OUD) treatment after discharge. Translating existing BUP induction and treatment strategies by taking advantage of the unique and well-established pharmacological properties of BUP has the potential to mitigate the aforementioned barriers to ED-initiated BUP. This study aims to evaluate the feasibility, acceptability, safety, and utility of the rapid loading induction strategy in the ED. Demonstrating that this efficacious pharmacotherapy can be initiated practically in the ED as a bridge to ongoing BUP treatment would support the efforts to expand the delivery and impact of evidence-based opioid treatment. We hypothesize that enrollment of 35 ED patients with OUD and opioid withdrawal in an open-label, single arm study of a BUP 32mg loading dose induction will provide necessary information on feasibility, utility, and identification of optimal processes for the development of a treatment initiation protocol suitable for the ED setting so that we can properly plan subsequent large-scale clinical trials.

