## 4 Study Design and Endpoints

### 4.1 Description of Study Design

This is an open-label, single arm, single site feasibility and acceptability study in which 35 ED patient-participants who have untreated moderate to severe OUD and are experiencing opioid withdrawal (COWS score  $\geq 8$ ). will receive treatment in the ED with a loading dose of BUP 32mg SL (administered in divided doses) at their index visit. We will assess the feasibility, acceptability, safety, and utility of this intervention and provide preliminary data on the effect on opioid withdrawal, craving, and sedation as well as additional patient-level outcomes (engagement in treatment, drug use, quality of life, healthcare utilization).

The first assessment will occur in-person in the ED at the index visit (day 0), and 4 additional appointments will be scheduled: 3 research visits and one follow-up care appointment with an OUD provider. Research assessments will be conducted in-person at clinical research space on Bellevue/NYULH campus on days 1-3, and by phone on day 30. Patients will be provided with appointment reminder cards with the time and location of their next appointment, and the contact information for the research study team. At the conclusion of their day 3 visit, participants will be given a prescription for BUP SL 16mg per day with a quantity sufficient to last until their scheduled clinical follow up appointment for ongoing treatment. The prescription will be provided earlier, at the day 1 or day 2 research visit, if the participant reports opioid withdrawal and/or craving and has objective signs of withdrawal at that time.

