#### 3. To assess the duration of effect of BUP 32mg SL on treating opioid withdrawal and craving (days 1-3).

We will generate appropriate descriptive statistics using the aforementioned validated objective, subjective, and physiologic measures of opioid withdrawal, craving, and drug effects on days 1-3. We will generate proportions for the number of participants who report withdrawal, report craving, have objective signs of withdrawal, return to use of other opioids, and/or require prescription for BUP on days 1-3 and estimate the time to occurrence and confidence intervals for these events.

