## 10 Statistical Considerations

### 10.1 Statistical and Analytical Plans (SAP)

The overall findings of the study will be used to assess the feasibility, acceptability, and utility of initiating a BUP loading dose in ED patients and linking patients to ongoing OUD treatment. Statistical analyses will consist of descriptive analyses for the primary outcome (proportion of participants successfully induced via loading dose), and secondary outcome measures (opioid withdrawal and craving scores, time to next BUP dose, opioid and other illicit drug use, proportion making a successful transition to an outpatient clinic). Measures of central tendency (the mean), and the variability (standard deviation) of the study participant characteristics and for other participant-reported or objectively evaluated measures will also be calculated. Summary tabulations and measures of central tendency, variance, and other distributional properties of the obtained results will be presented. Where applicable, we will also conduct cross-tabulations and comparative analyses of variance based on selected key characteristics of the study participants (e.g., sex, age categories, baseline opioid requirement). This is a pilot study aimed at producing preliminary data which will inform future large-scale studies. Our analyses will be purely descriptive and we will not attempt to show an effect size, thus there is no power calculation for this sample size, it is based on feasibility.

Our a priori hypotheses of the potential effect of patient characteristics on outcomes will be tested in subsequent large scale studies. The outcomes obtained in the proposed pilot study will also be compared with benchmark data based on the results of our previous studies with similar patient populations and other available recent or contemporaneous research and clinical data. Adverse events recorded in the study will be reported using both quantitative tabulations and qualitative descriptions.

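### No rule covers participants still free of withdrawal and craving at Day 3, although the cited durations make many such participants likely and section 10.1 names only a mean and SD

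*Combined protocol and SAP*

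**What the plan says.** **Expected duration.** Section 2.1.2 of the combined protocol and SAP gives four figures:

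- After 24 mg, "withdrawal suppression lasted >72 hours".
- After 32 mg, nine of ten heroin users "completed detoxification with negligible withdrawal symptoms, with suppression also lasting > 3- 4 days".
- In a single case given 120 mg, "Withdrawal suppression persisted for 4 days after initial administration".
- For craving, in a randomised trial of 32, 64 and 96 mg, "The resolution of craving was maintained at 5 days post initial treatment".

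The dose rationale in section 2.1.3 is more cautious: "A 32mg SL dose of BUP may provide effective treatment for over 24 hours or more".

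**Observation.** Section 3.2 (objective 4) and section 5.1.2 item 3 set the duration endpoint on Days 1-3. Section 4.1 states: "At the conclusion of their day 3 visit, participants will be given a prescription for BUP SL 16mg per day". Section 6.9.4 adds that participants with no withdrawal at any of those visits are told to start that prescription themselves once withdrawal or craving emerges. The next scheduled contact is the Day 30 call (sections 1.1.1 and 7.4.4).

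**Analysis.** Section 5.1.2 item 3 plans proportions with each event on Days 1-3 and will "estimate the time to occurrence and confidence intervals for these events". It names no estimator and no censoring rule. Section 10.1 lists time to the next buprenorphine dose among the secondary outcomes. The specific summaries it names are "Measures of central tendency (the mean), and the variability (standard deviation) of the study participant characteristics and for other participant-reported or objectively evaluated measures", followed by a general reference to tabulations and other distributional properties.

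**The concern.** Daily assessment ends at about the point where the cited withdrawal-suppression times begin. For a participant who is event-free at Day 3, both the return of symptoms and the next dose fall in a period with no scheduled contact until Day 30. All that is known from the daily visits is that the time exceeds about 72 hours. A mean and SD cannot be computed validly from such data without a rule for the unobserved part. The two obvious shortcuts, leaving those participants out or entering 72 hours for them, both pull the mean down.

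How long 32 mg lasts is the reason for studying a loading dose as a bridge to follow-up care, and the pilot is meant to inform a larger trial. A mean built on either shortcut would also hide differences: a longer-lasting effect would look much like a shorter one.

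**Working it through.** The documents state no duration estimate, event count or distribution, so there is no figure of theirs to reproduce. The check asks how many participants would be censored, and how far a naive mean would move, under stated assumptions.

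**Inputs from the documents.** Last daily assessment at Day 3, taken as C = 72 h. N = 35 enrolled (section 6.6). Cited withdrawal suppression of more than 72 h (24 mg) and more than 3-4 days (32 mg). The rationale's own expectation of 24 hours or more.

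**Assumption.** Lognormal times with median m and SD of log time s = 0.4 to 0.6. The median of 84 h is 3.5 days, the middle of 3-4 days. Medians of 24 and 36 h represent the cautious expectation.

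**Formulas.** With z = (ln 72 - ln m)/s and Φ the standard normal distribution function:

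- event-free at 72 h = 1 - Φ(z)
- true mean = m·exp(s²/2)
- A = true mean × Φ(z - s), the part of the mean contributed by times up to 72 h
- mean of observed events only = A/Φ(z)
- mean with 72 h entered for the rest = A + 72 × (1 - Φ(z))

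**Worked case, m = 84 h, s = 0.4.** z = -0.1542/0.4 = -0.385, so 65.0% are event-free (0.650 × 35 = 22.8). True mean = 84 × exp(0.08) = 91.0 h. A = 91.0 × Φ(-0.785) = 91.0 × 0.216 = 19.7 h. Events only: 19.7/0.350 = 56.2 h. Capped: 19.7 + 72 × 0.650 = 66.5 h.

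**Results over s = 0.4 to 0.6.**

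| Median (h) | Event-free at 72 h | True mean (h) | Events only (h) | 72 h entered (h) | Capped mean against truth |
|---|---|---|---|---|---|
| 24 | 0.3-3% | 26-29 | 26-27 | 26-28 | 0 to -3% |
| 36 | 4-12% | 39-43 | 35-37 | 38-40 | -2% to -8% |
| 72 | 50% | 78-86 | 47-54 | 60-63 | -19% to -31% |
| 84 | 60-65% (21-23 of 35) | 91-101 | 49-56 | 63-67 | -27% to -37% |
| 96 | 68-76% | 104-115 | 51-58 | 65-69 | -34% to -43% |

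**Masking.** Moving the median from 72 to 96 h raises the true mean by 26-29 h, but either naive mean by only about 4-6 h.

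**Other distribution.** With Weibull times (shape 1 to 3), the capped mean is 15-50% low at a median of 72 h, 31-60% low at 96 h, and 0-25% low at 24-36 h. The direction agrees; the size depends on the shape.

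**Visit dating works the other way.** If onset is dated to the next daily visit and capped at 72 h, the Weibull result at medians of 24-36 h is between 6% too low and 49% too high.

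**Proportions.** The share event-free at Days 1, 2 and 3 does not depend on what happens after Day 3. If all 30 expected completers were event-free at Day 3, the exact 95% lower limit would be 0.025^(1/30) = 88.4%; for 35 of 35 it would be 90.0%.

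**The case against.** The strongest reply is that section 5.1.2 item 3, the text specific to this endpoint, does not prescribe a mean. It plans proportions and time to occurrence with confidence intervals, which fits a survival analysis. The mean and SD come from a general sentence in section 10.1, which also allows other distributional summaries. This stands. A reader might infer that the plan reports duration as a mean and therefore understates it. The documents do not support that, because nowhere do they say that event-free participants are dropped or set to 72 hours. With a proper censored analysis the estimate is truncated, not biased by the end of the window.

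A reader might also infer that no reported mean could exceed 72 hours. That does not follow. Time to the next buprenorphine dose has no stated Day 3 limit, and section 6.9.4 lets that dose fall later. Some information reaches past Day 3: 30-day timeline follow-back of opioid use, Day 30 withdrawal and craving measures, reported adherence, and reported unscheduled ED visits. Of these, none is stated to date the first return of withdrawal or the first prescribed dose.

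Nor should the sources be read as showing five days of withdrawal suppression at the study dose. The five-day figure is for craving in a trial of three doses; the four-day case received 120 mg; and the 32 mg withdrawal source had ten participants. If the true median is nearer 24-36 hours, few participants are censored. Craving or return to use may also occur before objective withdrawal.

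What remains is the missing rule: no passage says how participants event-free at Day 3 enter any time summary.

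**Conclusion.** The point holds as a gap in the analysis plan and not as a demonstrated bias. On the protocol's own sources, participants event-free at Day 3 are foreseeable and may be half or more of the sample. Neither section 5.1.2 item 3 nor section 10.1 says how to treat them, and a mean and SD taken literally would be invalid for time to the next buprenorphine dose.

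The size is conditional on two things: that event-free participants are dropped or capped, and that durations are near those cited. Under both, with the lognormal assumption and a median of 84 hours, a true mean of 91-101 hours would appear as 49-56 or 63-67 hours. With a median of 24-36 hours, capping costs 0-8% under the lognormal and up to 25% under the Weibull. This concerns a secondary endpoint of a descriptive pilot; the primary endpoint is settled at the index visit and is unaffected. It is a cheap improvement worth making.

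**What to change.** In sections 5.1.2 item 3 and 10.1:

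- Treat a participant who is event-free at the last Day 1-3 contact as right-censored at that contact.
- Report Kaplan-Meier event-free proportions with 95% confidence intervals at Days 1, 2 and 3, and a median only if it is reached.
- Do not report a mean or SD for time to withdrawal, craving or the next buprenorphine dose.
- State that duration from the daily assessments is estimable only to about 72 hours.

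At the existing Day 30 call, ask for the date symptoms returned and the date of the first prescribed buprenorphine dose. Report both as recall data, separately from the daily assessments.

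The cost is a few lines of SAP wording, standard software and two dates on an existing call. No visit, treatment or sample size changes. The downsides are recall error in the Day 30 dates and no single average duration to quote.
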